9.3.2 Cautionary Medications

The following medications should be used with caution (see Appendix B):

- Drugs that are mild/moderate inhibitors or inducers of CYP3A, CYP2C8, PGP or BCRP because they may alter dabrafenib concentrations.

- *In vitro* dabrafenib inhibits CYP2C8, CYP2C9, and CYP2C19 activity. Concentration of medications metabolized by these enzymes may be altered by dabrafenib.
- *In vitro* dabrafenib induces CYP3A4, CYP2B6, CYP2C8, CYP2C9, and CYP2C19. Co-administration of dabrafenib and medications which are affected by the induction of these enzymes may result in loss of efficacy. If co-administration of these medications is necessary, investigators should monitor subjects for loss of efficacy or consider substitutions of these medications.

10.0 EVALUATION DURING TREATMENT/INTERVENTION

10.1 Standard Evaluation

Study participants will be evaluated at the start of each 4 week cycle (\pm 5 days, see Table 8). At these visits, patients will be assessed clinically for melanoma recurrence, toxicity, and performance status. A full physical examination with standard vital signs will also be performed in addition to an ECG and standard laboratories including a CBC, comprehensive metabolic panel, phosphorous, magnesium, and LDH. Radiographic evaluation of disease status will occur at the end of cycles 2 and 4. Dermatological exams (to assess toxicity and to screen for squamous cell carcinoma/keratoacanthomas) will also be done at the completion of cycles 2 and 4 or more frequently as indicated clinically. Ophthalmologic exams will be done at the completion of Cycle 1 and 3 or more frequently as indicated clinically. Dabrafenib will be discontinued after 4 cycles of adjuvant therapy or sooner for disease recurrence or the development of any of the conditions listed in Section 13.0.

After the completion of adjuvant dabrafenib, study participants will undergo active surveillance for disease recurrence. Patients will present at 6 months for a medical history, physical examination with standard vital signs, standard laboratories, and a radiographic evaluation of disease status. This assessment will be repeated every 3 months until the completion of the active follow-up period at 24 months from the date of surgical resection or at recurrence. These assessments and radiographic studies can occur 2 weeks earlier or later without being considered a protocol violation. After 24 months, patients who remain free of disease will continue to undergo routine follow-up and disease assessment at the discretion of their treating physician. Their charts will be reviewed by research staff biannually to monitor for disease relapse and survival and data collection will be limited to survival status until the completion of the study.

Table 8: Pre treatment Evaluation/Evaluation during Treatment

Cycle	Screen ¹	Adjuvant Dabrafenib ¹																Observation ⁿ			
		Cycle 1				Cycle 2				Cycle 3				Cycle 4				6	Every 3 months	24 months/ End of Study	Survival (every 6 months)
		1	2	3	4	5	6	7	8	9	10	11	12	13	14	15	16				
Month																					
Week																					
Medical History	X	X				X				X				X				X	X	X	
Pill Diary		X				X				X				X							
ECOG Performance Status	X	X				X				X				X				X	X	X	
Physical Exam ^a	X	X				X				X				X				X	X	X	
Laboratory Evaluation ^{b, c}	X	X				X				X				X				X	X	X	
ECG	X	X				X				X				X							
Radiologic Evaluation ^d	X							X ^k								X ^k		X	X	X	
Dermatology Evaluation ^h	X							X								X					
Ophthalmologic Evaluation ^h	X			X								X									
MRI Brain ^e	X																			X	
Tumor Biopsy ^f																				X	
Research Bloods ^g		X				X				X				X				X	X	X	
Survival Review																					X

- a: Complete physical examination with standard vital signs
- b: CBC, CMP, Phosphorous, Magnesium and LDH
- c: Serum β -HCG if applicable
- d: CT-C/A/P with contrast (preferred) or MRI with and without gadolinium (if contrast allergy) or PET scan with non-contrast CT of the chest (if below the knee melanoma primary)
- e: Contrast enhanced CT-head is an acceptable alternative
- f: Mandatory tumor biopsy at relapse of disease
- g: One 10cc lavender top, 2 cell-free DNA BCT tubes (Streck, Inc.), and 2 10 cc green top tubes at the first research blood draw; two 10cc green top tubes and 2 cell-free DNA BCT tubes (Streck, Inc.) thereafter as indicated on the study calendar.
- h: \pm 2 weeks
- i: Refer to Section 8.0, laboratories and ECG performed at screening do not need to be performed at Cycle 1, week 1 if these studies were completed within 7 days of Cycle 1, week 1.
- j: Treatment window \pm 5 days for each cycle
- k: \pm 1 week

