1.0 PROTOCOL SUMMARY AND/OR SCHEMA

Inhibition of $BRAF^{V600E}$ kinase has emerged as effective therapeutic strategy for patients with metastatic melanoma harboring a $BRAF^{V600E}$ mutation. It is reasonable to speculate that $BRAF^{V600E}$ kinase inhibitors will benefit molecularly selected melanoma patients at earlier stages of the disease. Patients with stage IIIC melanoma are at an extremely high risk of disease recurrence and death despite definitive surgical resection. Data from our Center indicate that the relapse-free survival (RFS) for stage IIIC disease is only 24% at 2 years. In this single center phase II trial, patients with surgically-resected stage IIIC melanoma characterized by a $BRAF^{V600E}$ or $BRAF^{V600K}$ mutation will be treated with 4 cycles of adjuvant dabrafenib and monitored clinically and radiographically for disease recurrence for 24 months following surgical resection. We will test the hypothesis that adjuvant $BRAF$ kinase inhibition will improve RFS from 24% to 51% at 24 months. The planned accrual is for 23 patients. The primary objective of the study will be to determine the RFS at 24 months. The trial would be considered positive if 9 or more patients are relapse-free and alive at 24 months. The trial would be terminated early if at any time 15 patients relapsed or died before 24 months. Secondary objectives include the assessment of dabrafenib toxicity and the determination of overall survival (OS). In an exploratory fashion, pretreatment tumors biopsies and biopsies at the time of relapse will be obtained to characterize the tumors genetically and to assess for mechanisms of resistance to $BRAF$ inhibition. Serial blood samples will also be obtained and used to determine if circulating tumor-derived exosomes can predict melanoma recurrence.

STUDY SCHEMA

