3.0 BACKGROUND AND RATIONALE

3.1 Regional metastatic melanoma

It is projected that there will be 76,250 new cases of cutaneous melanoma in the United States in 2012 [1]. Ten to 13% of patients with cutaneous melanoma will present with regional metastatic disease. Regional metastatic melanoma [American Joint Commission on Cancer (AJCC) Stage III disease] is defined by the neoplastic involvement of the regional lymph nodes and/or regional cutaneous disease in-transit. Independent prognostic factors for this stage of disease include the depth of the primary tumor, the presence of ulceration in the primary tumor, the number of tumor-bearing lymph nodes, and the burden of nodal disease [2]. Stages III patients are sub-classified into three groups (i.e. IIIA, IIIB and IIIC) by presence or absence of these important prognostic factors.

Definitive surgical resection is the only widely accepted modality for long-term disease control and cure. Even in the setting of a complete surgical resection, the risk of disease recurrence and death is extremely high, particularly for patients with stage IIIC disease. Data from our Center show that the 5-year relapse-free survival for stage IIIC melanoma is 15%; the 5-year overall survival is only 11% [3]. This indicates that relapse is almost equivalent to death in patients with stage IIIC melanoma. Preventing disease relapse is thus a key objective.

Patients with surgically resectable stage IIIC melanoma have few tolerable and effective systemic therapies available to alter the natural history of their disease. Adjuvant high dose and pegylated interferon therapy have been shown to offer a modest relapse-free survival benefit in randomized studies [4, 5]. Unfortunately, interferon-based adjuvant therapy is poorly tolerated and no study has demonstrated an overall survival advantage [4-7]. As such interferon is not uniformly accepted as a standard of care, despite being the only FDA approved agent for use in the adjuvant setting. Clinical trials of adjuvant immunotherapies,

vaccines and chemotherapies have also been disappointing and have not modified the risk of recurrence or death from melanoma after definitive surgical resection [8].

As surgically resectable stage IIIc melanoma has a high mortality with minimal effective treatments, novel adjuvant and neoadjuvant therapies are clearly necessary to improve patient outcomes.

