12.0 CRITERIA FOR THERAPEUTIC RESPONSE/OUTCOME ASSESSMENT

12.1 Assessment of Relapse Free Survival

Relapse free survival is defined as the time from surgical resection to the first recurrence or death as assessed by physical examination and radiographic evaluation. All recurrences will be confirmed by biopsy and histologic evaluation.

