14.0 BIOSTATISTICS

This is a single institution phase II trial assessing the efficacy of adjuvant dabrafenib (GSK2118436) in patients with surgically resected AJCC stage IIIc melanoma characterized by a *BRAF*^{V600E/K} mutation. The primary endpoint is 24 month relapse-free survival rate. Patients will be enrolled within 90 days of surgical resection and monitored clinically and radiographically for relapse for recurrence for 24 months. Data from our Center indicate that the relapse-free survival (RFS) for stage IIIc disease is only 24% at 2 years.

A single stage design will be employed whereby a 24% relapse-free rate at 24 months is considered not promising, a 51% relapse-free rate at 24 months is considered promising, and the probabilities of a type I error (falsely accepting a non-promising therapy) and type II error (falsely rejecting a promising therapy) are set at 0.10 and 0.10, respectively. Twenty-three patients will be accrued. All patients will be followed for a minimum of 24 months. At the end of the trial, if 9 or more patients are relapse-free at 24 months out of a total of 23 patients then the treatment will be considered worthy of further investigation. If 8 or fewer patients are relapse-free at 24 months in then the treatment will be declared negative. The trial would be terminated early if at any time 15 patients relapsed or died before 24 months. This design yields a 0.90 probability of a positive result if the true relapse-free survival is at least 51% and yields a 0.90 probability of a negative result if the true relapse-free survival is 24%.

With the exception of those patients who elect to withdraw consent, all patients will be followed with an intention-to-treat and will be evaluated for the primary endpoint as per the protocol study calendar. This includes patient who develop unacceptable toxicity from the agent, secondary malignancies, or an intercurrent illness as listed in section 13.0. Patients who elect to withdraw consent will be evaluated as follows. If patients relapse on study before withdrawing consent (failure), or if they withdraw consent after month 24 without relapsing (success), they are counted as events. If patients withdraw consent before month 24 and before they relapse, then they are not events and will be replaced. Patients, who are lost to follow up at 24 months or later, are counted as successes and will be censored beyond that point.

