Toxicities will be tabulated according to the NCI Common Toxicity version 4.0. Overall survival and relapse-free survival will be estimated using Kaplan-Meier methodology. Overall survival will be assessed from surgical resection to death or last follow-up; relapse-free survival will be assessed from surgical resection to relapse, death or last follow-up. Explorative correlative studies examining the genetic heterogeneity of *BRAF*-mutated melanoma, genetic mechanisms of intrinsic and acquired resistance to dabrafenib, and circulating tumor-derived exosomes as a biomarker of disease recurrence will be reported in a descriptive manner.

A total of 23 patients will be accrued to this study. Enrollment is anticipated to take 6 to 12 months and the study is expected to be completed in 30 to 36 months.

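### Does a relapse first found at a late month-24 visit need a written dating rule?

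*Combined protocol and SAP*

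**What the plan says.** Section 12.1 defines relapse-free survival as "the time from surgical resection to the first recurrence or death as assessed by physical examination and radiographic evaluation". The next sentence reads: "All recurrences will be confirmed by biopsy and histologic evaluation". Section 10.1 schedules surveillance every three months up to month 24 from resection and allows a window: "These assessments and radiographic studies can occur 2 weeks earlier or later without being considered a protocol violation". The month-24 assessment is the last scheduled study scan.

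Section 14.0 makes the trial positive if at least 9 of 23 patients are relapse-free at 24 months. Section 1.0 puts it this way: "The trial would be considered positive if 9 or more patients are relapse-free and alive at 24 months". Section 14.0 also says that patients, other than those who withdraw consent, "will be evaluated for the primary endpoint as per the protocol study calendar". The early-termination rule is separate: "The trial would be terminated early if at any time 15 patients relapsed or died before 24 months". For the time-to-event summaries, "Overall survival and relapse-free survival will be estimated using Kaplan-Meier methodology", with time measured from surgery.

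Section 14.0 settles withdrawal of consent and loss to follow-up around month 24. It does not say which date a relapse takes when it is first detected at that visit.

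**The concern.** Take a patient whose month-24 scan is done ten days late, within the window, and shows a new lesion that biopsy confirms. By the study calendar this is a relapse found at the month-24 assessment. By the literal words of the early-termination rule it did not happen before 24 months. That rule mirrors the final cut-off (23 − 9 + 1 = 15), so one would expect both to use the same definition of failure. If the biopsy date counted, even an on-time scan would give a relapse date after month 24.

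The decision is a count, so one patient can reverse it: 8/23 = 34.8% is negative and 9/23 = 39.1% is positive. In a single-arm trial it is better not to choose such a convention after seeing outcomes. The Kaplan-Meier estimate at 24 months could also differ from the count by 1/23 = 4.3 points for each such patient, if no one is censored earlier.

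**Working it through.** **1. The plan's own figures.** Inputs from Section 14.0: n = 23, cut-off 9, null rate 0.24, target rate 0.51, both error limits 0.10. Exact binomial:

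- Type I error: P(X ≥ 9 | 23, 0.24) = 0.0776.
- Power: P(X ≥ 9 | 23, 0.51) = 0.9115.

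The design meets its limits, with 0.022 to spare on type I error and 0.011 on power.

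**2. Curves near month 24.** The documents give no hazard around month 24, so these are assumptions. Curves A to C pass through 24% at 24 months (Section 14.0) and 15% at 5 years (Section 3.1). Curve D uses only the 24%.

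- A: constant hazard after month 21, ln(0.24/0.15)/36 = 0.01306 per month.
- B: Weibull, shape 0.311.
- C: exponential plus cured fraction, cured 0.1466, rate 0.0922 per month.
- D: exponential throughout.

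**3. The window alone, read by the study calendar.** A relapse found at the month-24 visit is a failure. A late scan can then add only relapses arising in the two weeks (0.46 month) after month 24. An early scan can miss only those arising in the two weeks before. Extreme cases, with every scan shifted the same way (power assumes proportional hazards, ratio ln 0.51 / ln 0.24 = 0.472):

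| Curve | S(24) − S(24.46) | Patients of 23 | Type I, all late | Power, all late | Type I, all early | Power, all early |
|---|---|---|---|---|---|---|
| A | 0.0014 | 0.03 | 0.075 | 0.909 | 0.080 | 0.914 |
| B | 0.0020 | 0.05 | 0.074 | 0.908 | 0.081 | 0.915 |
| C | 0.0039 | 0.09 | 0.071 | 0.905 | 0.085 | 0.918 |
| D | 0.0065 | 0.15 | 0.067 | 0.901 | 0.090 | 0.921 |

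Every cell stays inside 0.10 and 0.90. With scans on time, the figures are those of step 1.

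**4. The adverse reading.** Suppose instead that relapses arising in months 21 to 24 and first found at the last visit were dated after month 24 and scored as successes. The share at risk is d = S(21) − 0.24. Type I error is P(X ≥ 9 | 23, 0.24 + f·d), where f is the fraction rescored:

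| Curve | d | Patients of 23 | f = ¼ | f = ½ | f = 1 |
|---|---|---|---|---|---|
| A | 0.0096 | 0.22 | 0.082 | 0.086 | 0.095 |
| B | 0.0143 | 0.33 | 0.084 | 0.091 | 0.105 |
| C | 0.0298 | 0.68 | 0.091 | 0.106 | 0.141 |
| D | 0.0469 | 1.08 | 0.100 | 0.126 | 0.188 |

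The column f = 1 requires that every such relapse be dated after month 24 (by biopsy, or by a late scan with the before-24-months wording applied literally) and that none be found sooner from symptoms. It also requires that the historical 24% was dated by a different convention. If that figure was also dated at detection, much or all of the rise disappears. The documents do not say.

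**5. Which reading the text supports.** The words about events before 24 months belong to the early-termination rule. The final rule asks who is relapse-free at 24 months, and Section 14.0 sends that evaluation to the study calendar, where Table 8 has a month-24 column with imaging. Section 12.1 makes examination and imaging the means of assessing recurrence, and biopsy confirms what they found. Scan dating alone would not settle a late scan; the calendar wording does. Step 3 therefore applies, and step 4 does not.

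**The case for a change.** The best argument for a change is that the convention really is unwritten, costs little to write, and sits on a count where one patient decides. Under the adverse reading the 0.10 limit can be exceeded. Table 8 also appears to place the only brain imaging after screening at month 24 (its layout is broken in the text available), so more relapses may first surface there than the curves suggest. All of this is true as far as it goes. The step 4 values cannot be capped at 0.141 either, because they move with the assumed late hazard. The 15% anchor is itself uncertain, since Section 3.1 gives a 5-year overall survival of 11%, below the relapse-free figure.

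But the adverse reading asks an analyst to look at a biopsy-proven relapse found at the protocol's month-24 assessment and call the patient relapse-free at month 24. Section 14.0 gives no support for that. The early-termination rule might reach its fifteenth event without such a patient, but the final count still scores the patient a failure, so the verdict does not change. The Kaplan-Meier curve has no decision role.

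A written rule could also do harm. If success were judged only at the month-24 assessment, a patient scanned clean at 23.5 months who relapsed clinically before month 24 would become a success. The present text scores that patient a failure.

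**Conclusion.** No change follows. The gap is real but small, and the plan's own wording fills it: a relapse first found at the month-24 assessment, within its window and confirmed by biopsy, is a failure. On that reading the design keeps type I error 0.078 and power 0.911 with scans on time. With every scan two weeks late or every scan two weeks early, the ranges are 0.067 to 0.090 and 0.901 to 0.921. The expected number of patients in the two weeks after month 24 is 0.03 to 0.15 of 23 under the null. These sizes rest on assumed curves near month 24 and, for power, on proportional hazards. The conclusion that the text does not score the endpoint in two contradictory ways rests on Sections 12.1 and 14.0 alone.

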10.2 Correlative Studies and Tumor Biopsies at Progression of Disease

Pre-treatment tumor material will be available from the biopsy used to establish that the patient had stage IIC melanoma or from the initial surgical resection of residual disease. In patients who relapse, the standard of care is to obtain a biopsy to confirm progression. This will also be available. Biopsies will be performed either by the Principal Investigator or staff members from surgery, dermatology, or interventional radiology. Tissue samples will either be collected from the Tissue Procurement Service (TPS) after appropriate pathological review or directly delivered to the [name] Lab by a Research Study Assistant or lab member. We shall coordinate samples within Pathology through [name] and/or any other appropriate members of the pathology service. Tissue samples will be analyzed with the appropriate assays described in this protocol, and stored in the Immune Monitoring Facility in the Zuckerman Research Building under the supervision of [name] and [name].

In addition, peripheral blood will be obtained on the first day of therapy and then every 3 months for the duration of the study. One 10cc lavender top tube and 2 10cc green top tubes of peripheral blood will be collected on the first day of treatment. The lavender top tube will be utilized to extract germline DNA to serve as a control for the genetic analyses described below. This tube of blood will be delivered by the research staff to the [name] Lab for storage and processing as described below. The green top tubes and all additional research bloods will be used for exosomes analysis. These blood samples will be delivered to the laboratory of [name] for storage and processing as described below.

DNA from pretreatment tumor, germline DNA from peripheral blood, and tumor DNA from progressing melanoma will be analyzed. These studies will be performed in the laboratory of [name] and [name] using an exon capture assay. This assay, designed by [name], currently sequences all coding exons of 230 cancer-associated genes including *PTEN*, *PIK3CA*, *AKT1*, *RB1*, *NF1*, *TP53*, *ERBB4* and others. In brief, tumor and normal DNA from each patient is used to generate a bar-coded library for sequencing analysis. Libraries are then subjected to exon capture of all coding exons for the 230 gene panel using custom-designed probes generated using the Agilent SureSelect Target Enrichment system [31]. Hybridized DNA is then sequenced using Illumina HiSeq 2000 instrumentation to generate paired-end 75-bp reads. Read pairs are assigned to the corresponding tumor samples according to the identity of each barcode and then aligned to the reference human genome (hg19) using the BWA algorithm [36], and performance metrics are calculated using the publically available suite of Picard tools (<http://picard.sourceforge.net>). Sequence variants, sequence coverage, and copy number alterations in tumor samples are determined using additional algorithms developed by the Medical and Population Genetics and Cancer Genome Analysis groups at the Broad Institute, including the Genome Analysis Toolkit (GATK) [37, 38]. Both tumor and matching normal DNA are analyzed simultaneously to identify germline single nucleotide polymorphisms (SNPs). In preliminary studies, we have generated average mean read coverage of over 500X using a DNA input of 250-500

nanograms. Importantly, this assay can be carried in FFPE-derived DNA, underscoring the utility of exon capture sequencing in identifying genetic aberrations from FFPE tissue.

Exosome analysis will be completed in the laboratories of Drs. [name] and [name]. Exosomes will be purified and analyzed as previously described [34]. Briefly, fresh or frozen human plasma will be isolated by centrifugation followed by serial ultracentrifugation with or without filtration. The LM10 nanoparticle characterization system (NanoSight) will be used for real-time analysis of particle size, concentration and aggregation. Exosomes will be further characterized by multiple methods including flow cytometry, immunoblotting, electron microscopy, reverse phase high pressure liquid chromatography with mass spectrometry (HPLC-MS), and gene expression profiling analysis. Importantly, the concentrations of exosomal levels of TYRP2, VLA-4, HSP70, and the MET oncoprotein will be determined over time in each patient in an effort to prospectively evaluate exosomal content as biomarker of melanoma recurrence.

Two tubes of blood (cell-free DNA BCT tubes (Streck, Inc.) or another appropriate tube for cFDNA) will be collected pre-treatment and every time research bloods are collected thereafter as shown in Table 8, in order to measure circulating tumor-derived DNA. Plasma will be stored until needed. DNA will be extracted from plasma and analyzed by digital PCR in the Genomics Core Laboratory ([name], head). Probes will be used specific for both mutated and wild-type BRAF V600E or V600K to allow quantification of tumor-derived and non-tumor-derived DNA. The hypothesis to be tested is that detection of circulating tumor-derived DNA will be an accurate measure of tumor recurrence.

